### **3.4 Concomitant Treatments**

#### **3.4.1 Prohibited and/or Restricted Treatments**

The following medications are prohibited during the study (unless utilized to treat a drug related AE):

- Immunosuppressive agents
- Immunosuppressive doses of systemic corticosteroids (except as stated in Section 3.4.3)
- Any concurrent anti-neoplastic therapy (ie, chemotherapy, hormonal therapy, immunotherapy, extensive, non-palliative radiation therapy, or standard or investigational agents for treatment of NSCLC)
- Any botanical preparation (eg herbal supplements or traditional Chinese medicines) intended to treat the disease under study or provide supportive care. Use of marijuana and its derivatives for treatment of symptoms related to cancer or cancer treatment are permitted if obtained by medical prescription or if its use (even without a medical prescription) has been legalized locally.

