#### **3.4.3 Permitted Therapy**

Subjects are permitted the use of topical, ocular, intra-articular, intranasal, and inhalational corticosteroids (with minimal systemic absorption). Adrenal replacement steroid doses > 10 mg daily prednisone are permitted. A brief (less than 3 weeks) course of corticosteroids for prophylaxis (eg, contrast dye allergy) or for treatment of non-autoimmune conditions (eg, delayed-type hypersensitivity reaction caused by a contact allergen) is permitted.

Regular concomitant use of bisphosphonates and RANK-L inhibitors for prevention or reduction of skeletal-related events in patients with bone metastases is allowed if initiated prior to first dose of study therapy. Prior palliative radiotherapy must have been completed at least 2 weeks prior to randomization.

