- Any event that leads to interruption in dosing lasting > 6 weeks from the previous dose requires discontinuation, with the following exceptions:
  - Dosing delays to allow for prolonged steroid tapers to manage drug-related adverse events are allowed.
  - Dosing delays lasting > 6 weeks from the previous dose that occur for non-drug-related reasons may be allowed if approved by the BMS Medical Monitor (or designee).
- Any AE, laboratory abnormality, or intercurrent illness which, in the judgment of the Investigator, presents a substantial clinical risk to the subject with continued nivolumab dosing.

Prior to re-initiating treatment in a subject with a dosing delay lasting > 6 weeks, the BMS Medical Monitor (or designee) must be consulted. Tumor assessments should continue as per protocol even if dosing is delayed. Periodic study visits to assess safety and laboratory studies should also continue every 6 weeks or more frequently if clinically indicated during such dosing delays.

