## **APPENDIX 2      MANAGEMENT ALGORITHMS**

These general guidelines constitute guidance to the Investigator and may be supplemented by discussions with the Medical Monitor representing the Sponsor. The guidance applies to all immuno-oncology agents and regimens.

A general principle is that differential diagnoses should be diligently evaluated according to standard medical practice. Non-inflammatory etiologies should be considered and appropriately treated.

[figure not shown]
Corticosteroids are a primary therapy for immuno-oncology drug-related adverse events. The oral equivalent of the recommended IV doses may be considered for ambulatory patients with low-grade toxicity. The lower bioavailability of oral corticosteroids should be taken into account when switching to the equivalent dose of oral corticosteroids.

Consultation with a medical or surgical specialist, especially prior to an invasive diagnostic or therapeutic procedure, is recommended.

The frequency and severity of the related adverse events covered by these algorithms will depend on the immuno-oncology agent or regimen being used.

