6.3 Populations for Analyses

- All enrolled subjects: All subjects who sign an informed consent form and are registered into the IWRS.
- All randomized subjects: All enrolled subjects who are randomized to 240 mg every 2 weeks or 480 mg every 4 weeks. This is the primary population for efficacy analyses. Analyses of demography and baseline characteristics, as well as outcome research, will be performed on this population, grouped as randomized.
- Per-protocol subjects: All randomized subjects who have no major protocol deviations. The relevant protocol deviations include the programmable deviations from inclusion and exclusion criteria at study entrance and administration of prohibited medications during the study. Non-programmable relevant eligibility and on-treatment protocol deviations, as well as significant (both programmable and non-programmable) eligibility including those subjects with untreated, symptomatic CNS metastases who should be excluded and on-treatment protocol deviations will be reported through a PPD tracking system - Clinical Trial Management System (CTMS). The details of relevant protocol deviations are described in [Section 7.2.2](#). The primary efficacy endpoint will be analyzed for this population as a sensitivity analysis.
- All treated subjects: All randomized subjects who receive at least 1 dose of nivolumab. This is primary population for safety analyses.

- 

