7.2.2 Relevant Protocol Deviations

The relevant protocol deviations will be summarized for all randomized subjects, by treatment arm and total. The following programmable deviations from inclusion and exclusion criteria will be considered as relevant protocol deviations. Non-programmable relevant eligibility and on-treatment protocol deviations, as well as significant (both programmable and non-programmable) eligibility including those subjects with untreated, symptomatic CNS metastases who will be excluded and on-treatment protocol deviations will be reported.

Eligibility at entrance:

- Subjects without histologically or cytological documented Sq.- or non-SqNSCLC who present with Stage IIIB/IV disease
- Subjects had received and tolerated nivolumab 3 mg/kg or 240 mg every 2 weeks for more than 12 months
- Subjects without at least 2 consecutive tumor assessments confirming CR, PR, or SD to the pre-study nivolumab treatment (latest scan must be performed within 28 days prior to randomization)

- Subjects without measurable disease by computed tomography (CT) or magnetic resonance imaging (MRI) per RECIST 1.1 criteria at the time of starting the first dose of pre-study nivolumab treatment
- Subject with baseline ECOG performance status > 2

On-Study:

- Subjects receiving concurrent antineoplastic therapy (i.e., chemotherapy, hormonal therapy, immunotherapy, extensive, non-palliative radiation therapy, or standard or investigational agents for treatment of NSCLC)
- Subjects receiving immunosuppressive agents.
- Subjects receiving immunosuppressive doses of systemic corticosteroids (except as stated in the Clinical Protocol Section 3.4.3).
- Subjects receiving treatment other than the randomized treatment

A by-subject listing of relevant protocol deviations will also be produced.

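### SAP 7.2.2 omits the protocol's exemption for treating drug-related AEs, so permitted immunosuppressant use is listed as a relevant deviation and may remove subjects from the per-protocol PFS analysis

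*SAP*

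**What the plan says.** **The protocol rule.** Protocol 3.4.1 opens its list with "The following medications are prohibited during the study (unless utilized to treat a drug related AE"). That lead-in governs every item below it, including immunosuppressive agents and immunosuppressive doses of systemic corticosteroids. The corticosteroid item then carries a second, separate exception for whatever Section 3.4.3 allows.

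**What Protocol 3.4.3 allows.** It covers locally acting steroids, adrenal replacement, and "A brief (less than 3 weeks) course of corticosteroids for prophylaxis (eg, contrast dye allergy) or for treatment of non-autoimmune conditions". It does not mention treatment of drug-related AEs.

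**The SAP deviation list.** Among on-study relevant deviations, SAP 7.2.2 has "Subjects receiving immunosuppressive agents", with no exception, and "Subjects receiving immunosuppressive doses of systemic corticosteroids (except as stated in the Clinical Protocol Section 3.4.3"). The deviations are summarized by arm for all randomized subjects and listed by subject.

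**The per-protocol set.** SAP 6.3 defines it as "All randomized subjects who have no major protocol deviations". It counts "administration of prohibited medications during the study" among the relevant deviations and refers to 7.2.2 for details. SAP 7.5.3 repeats the PFS analyses of 7.5.1 in this set, and SAP 7.3.2 summarizes its baseline characteristics.

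**The concern.** The SAP list follows the protocol's items closely and keeps the cross-reference to 3.4.3, but loses the lead-in that exempts treatment of a drug-related AE. A rule meant to detect departures from the protocol would therefore flag conduct that the protocol allows.

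Two things are at stake. First, the deviation summary and listing would overstate non-compliance. Second, subjects may leave the per-protocol set because of something that happened after randomization and was caused by study treatment. A set selected in that way is no longer a comparison of the randomized groups. Those excluded need not have the same PFS as those who stay: someone who progresses or dies early has less time to have such an event, while a toxicity that needs immunosuppression may itself go with a different course. The documents do not settle the direction.

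**Working it through.** **Part 1. The passages side by side**

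| Use | Protocol 3.4.1 with 3.4.3 | SAP 7.2.2 as written |
|---|---|---|
| Immunosuppressive agent for a drug-related AE | Exempt (3.4.1 lead-in) | Deviation |
| Immunosuppressive-dose systemic steroid for a drug-related AE, outside 3.4.3 | Exempt (3.4.1 lead-in) | Deviation |
| Steroid use covered by 3.4.3 | Exempt | Exempt |
| Either class for a reason covered by neither exemption | Prohibited | Deviation |

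The two documents differ in the first two rows only. Those rows are foreseeable use:

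- Protocol Appendix 2 states: "Corticosteroids are a primary therapy for immuno-oncology drug-related adverse events".
- Protocol 4.5.3 states: "Dosing delays to allow for prolonged steroid tapers to manage drug-related adverse events are allowed".
- SAP 7.4.2.1 accepts the same tapers as a reason for a long interruption.
- SAP 7.6.6 makes treatment with immune-modulating medication part of the definition of a non-endocrine immune-mediated AE. That definition applies regardless of causality, so these events overlap with drug-related AEs but are not the same group.

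**Part 2. Precision if subjects are excluded**

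The plan states no figure for this point, so there is none to reproduce. Inputs from SAP 5: about 350 subjects, hence 350/2 = 175 per arm, and assumed PFS rates S = 0.48 at 12 months and 0.63 at 6 months. The exclusion share p is an assumption. No document reports immunosuppressant use for drug-related AEs. Simplifications: equal rates in the arms, no censoring before the milestone, no stratification.

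Half-width of the one-sided 95% interval = 1.645 × √(2·S·(1−S)/n), with n = 175·(1−p).

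At 12 months, 2 × 0.48 × 0.52 = 0.4992:
- p = 0: 1.645 × √(0.4992/175) = 8.8 points
- p = 5%: 1.645 × √(0.4992/166.25) = 9.0 points
- p = 10%: 1.645 × √(0.4992/157.5) = 9.3 points
- p = 20%: 1.645 × √(0.4992/140) = 9.8 points

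At 6 months, 2 × 0.63 × 0.37 = 0.4662:
- p = 0: 1.645 × √(0.4662/175) = 8.5 points
- p = 5%: 1.645 × √(0.4662/166.25) = 8.7 points
- p = 20%: 1.645 × √(0.4662/140) = 9.5 points

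**Part 3. What bias would need**

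If a share p of an arm is excluded and those subjects have PFS rate Sx, the remaining rate is (S − p·Sx)/(1−p). Any shift in the difference therefore depends on p and Sx in each arm, all unknown. For scale only, take S = 0.48 in both arms, with 10% excluded in Arm 1 and 15% in Arm 2 (all assumed):

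- Sx = 0.68: Arm 1 (0.48 − 0.068)/0.90 = 0.4578; Arm 2 (0.48 − 0.102)/0.85 = 0.4447; difference −1.3 points.
- Sx = 0.28: Arm 1 (0.48 − 0.028)/0.90 = 0.5022; Arm 2 (0.48 − 0.042)/0.85 = 0.5153; difference +1.3 points.

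A 5-point imbalance combined with a 20-point outcome gap moves the difference by 1.3 points, in either direction.

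**The case against.** The strongest answer is that the documents already resolve this. Use that Protocol 3.4.1 permits is not a deviation at all. SAP 6.3 names prohibited medications, and Protocol 3.4.1 defines what is prohibited, exemption included. The SAP elsewhere treats this medication as expected and reports it separately (7.4.2.1, 7.6.6, 7.6.9). The word major in 6.3 may also be narrower than relevant in 7.2.2. The programming specification and the deviation-tracking rules are not public and may already be right.

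Part of this stands: removal from the per-protocol set cannot be taken as given. But 6.3 refers to 7.2.2 for the details, not to Protocol 3.4.1, and never says which items are major, so two programmers could build different sets. The mislabelling in the deviation summary and listing does not depend on how 6.3 is read.

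The scope is also narrower than a reader might infer. Only immunosuppressive agents and immunosuppressive steroid doses are caught, not every steroid course, and 3.4.3 already exempts some use. Nor does the protocol mandate the treatment: Appendix 2 describes its algorithms as guidance. Permitted is the accurate word.

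**Conclusion.** The omission is real and shows in the text. As written, SAP 7.2.2 labels permitted treatment of drug-related AEs as a relevant deviation, and it may, though need not, remove those subjects from the per-protocol PFS sensitivity analysis.

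Severity is low. The primary efficacy population is all randomized subjects and is unaffected. SAP 7.5.1 ends by stating that power is insufficient to demonstrate non-inferiority and that a one-sided 95% interval will be given instead, so no non-inferiority decision rests on either set.

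On the assumed 5% to 20% exclusion, the 12-month half-width grows by 0.2 to 1.0 points. That range is not a bound in either direction. The drug-related Grade 3-4 AE rate that Protocol 1.4.2 gives for CA209057 (10.5%) might look like a usable figure, but it counts AEs of any kind, not steroid use, and lower-grade events may also be treated with steroids.

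A reader might infer that the per-protocol comparison is biased against one arm. The documents do not support this. They give no exclusion rate by arm and no outcome for such subjects, and Protocol 1.1 expects each study regimen to be similar in safety to 3 mg/kg every 2 weeks.

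**What to change.** - **SAP 7.2.2:** add to both the immunosuppressive-agent and the corticosteroid bullets the clause *unless used to treat a drug-related AE (Protocol 3.4.1)*. Identify such use by linking the medication record to an AE assessed as drug-related. The split in SAP 7.6.9 between AE management and other use is not enough, because it would also exempt treatment of unrelated AEs.
- **SAP 6.3:** add one sentence stating which 7.2.2 deviations remove a subject from the per-protocol set.

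The cost is two clauses, one sentence and one derived flag. Causality is already assessed for every AE (Protocol 6). Whether the case report form links medications to AEs cannot be seen from the documents, so records without a link would need manual review. The change alters no clinical rule. It should be made before the per-protocol set is fixed.

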7.3 Study Population

7.3.1 Subject Disposition

The total number of subjects enrolled (randomized or not randomized) will be presented along with the reason for not being randomized.

The number of subjects randomized but not treated along with the reason for not being treated will be tabulated by treatment arm as randomized. This analysis will be performed on the all randomized subjects only.

The number of subjects who discontinue treatment along with corresponding reason will be tabulated by treatment arm as treated.

Subject disposition data will also be presented in a by-subject listing.

7.3.2 Demographics and Other Baseline Characteristics

Descriptive statistics will be used to summarize the following demographics and baseline characteristics for all randomized subjects, as well as for per-protocol subjects, by treatment arm and total.

- Age (years)
- Age group (< 65, ≥ 65 - < 75, ≥ 75, ≥ 65)
- Gender, Race/Ethnicity, Region/ Country
- ECOG PS (0, 1, 2)
- Baseline weight (kg), height (cm)

- Baseline body mass index (BMI) (kg/m^2), which is calculated as (body weight in kilograms) / (height in meters)²
- Tumor histology (Sq/Non-Sq)
- Disease stage at initial diagnosis (Stage 0/IA/IB/IIA/IIB/IIIA/IIIB/IV)
- Time from initial disease diagnosis to randomization (< 1 year, 1-< 2 year, 2 - < 3 year, 3 -< 4 year, 4 - < 5 year, \geq 5 year)
- Cell type (Adenocarcinoma, Squamous Cell Carcinoma, Large Cell Carcinoma, Broncho-alveolar Carcinoma, Other)
- EGFR mutation status, ALK translocation status
- Tobacco use (current, former, never, unknown)
- All lesions (investigator tumor assessments at baseline): sites of disease, number of disease sites per subject
- Target lesions (investigator tumor assessments at baseline): presence of target lesions, site of target lesion, sum of diameters of target lesions.

7.3.3 Medical history - Concurrent diseases

General medical history will be reported as counts and percentages for all randomized subjects by treatment arm and total, and listed by subject.

7.3.4 Prior Therapy Agents

Prior therapy that was received prior to the nivolumab treatment before randomization will be summarized for all randomized subjects by treatment arm and total:

- Type of prior systemic therapy received
- Line of prior systemic therapies received (0, 1, 2, \geq 3)
- Setting of prior systemic therapy regimen received (adjuvant, metastatic disease, neo-adjuvant, locally advanced)
- Best response to prior systemic cancer therapy including adjuvant therapy or neo-adjuvant therapy (CR/PR vs. SD vs. PD)
- Best response to prior systemic cancer therapy in metastatic disease setting (CR/PR vs. SD vs. PD)
- Time from completion of most recent prior systemic cancer therapy to first dose of nivolumab treatment before randomization (< 3, 3 - < 6, \geq 6 months)
- Time from completion of prior adjuvant/neo-adjuvant therapy to first dose of nivolumab treatment before randomization (subjects who received prior adjuvant/neo-adjuvant therapy), (< 6 months and \geq 6 months)
- Prior surgery related to cancer (yes or no)

- Prior radiotherapy (yes/no, stop date, location)
- Time from completion of most recent prior radiotherapy to first dose of nivolumab treatment before randomization (<1, 1 - < 2, ≥ 2 months)
- Prior/current non-study medication classified by anatomic and therapeutic classes
- Prior systemic cancer therapy by therapeutic drug class and generic name.

Agents and medication will be reported using the generic name. A listing of prior systemic cancer therapy, radiotherapy and surgery related to cancer by subject will also be provided for all randomized subjects.

7.3.5 Baseline examinations

Subjects with abnormal baseline physical examination will be tabulated by examination criteria for all randomized subjects by treatment arm as randomized. A by-subject listing will be provided.

7.3.6 Stratification Factors

Summary tables by treatment arm for stratification factors (Histology [Sq vs. Non-Sq]; response criteria to pre-study nivolumab at randomization (CR or PR vs. SD) will be provided.

Summary tables (cross-tabulations) by treatment arm for stratification factor will be provided to show any discrepancies between what was reported through IWRS vs. CRF data (baseline).

7.4 Extent of Exposure

Analyses in this section will be performed by treatment arms as treated and in all treated subjects unless otherwise specified.

7.4.1 Administration of Study Therapy

Prior Nivolumab Therapy before Randomization

Prior to enrollment, subjects will have received up to 12 months (52 weeks) of nivolumab 3 mg/kg or 240 mg every 2 weeks (Q2W). The following parameters will be summarized (descriptive statistics) for prior nivolumab exposure before randomization for all randomized subjects:

- Relative dose intensity (%) using the following categories: < 50%; 50 - < 70%; 70 - < 90%; 90 - < 110%; ≥ 110%.
- Number of infusions received (summary statistics)
- Duration of prior nivolumab treatment before randomization

Table 7.4.1-1 summarizes the key parameters used to calculate dosing data.

Table 7.4.1-1: Administration of Prior Nivolumab Therapy Before Randomization: Definition of Parameters

Nivolumab	
Dosing schedule per protocol	3mg/kg every 2 weeks; 240 mg every 2 weeks
Number of infusions	Number of infusions captured in prior systemic therapy Case Report Form (CRF)
Relative dose intensity (%)	$\left[\frac{\text{Number of infusions}}{\{(\text{Last dose date} - \text{Start dose date} + 14) / 14\}} \right] \times 100$
Duration of treatment	Last dose date - Start dose date +1

On Treatment Nivolumab Therapy

At enrollment, subjects will be randomized to receive either 240 mg every 2 weeks (Arm 1) or 480 mg every 4 weeks (Arm 2). The following parameters will be summarized (descriptive statistics) for all treated subjects:

- Relative dose intensity (%) using the following categories: < 50%; 50 - < 70%; 70 - < 90%; 90 - < 110%; ≥ 110%.
- Number of doses received (summary statistics)
- Cumulative dose

Duration of treatment will be presented by treatment arm using a Kaplan-Meier curve whereby the last dose date will be the event date for subjects who discontinued study therapy. Subjects who are still on study therapy will be censored on their last dose date.

A by-subject listing of extent of exposure: weight, number of doses, date of first and last dose, cumulative dose, and relative dose intensity, duration of treatment, and reason for discontinuation will be provided.

Table 7.4.1-2 summarizes the key parameters used to calculate dosing data.

Table 7.4.1-2: Administration of Study Therapy: Definition of Parameters

Nivolumab	
Dosing schedule per protocol	240 mg every 2 weeks for Arm1, 480 mg every 4 weeks for Arm 2
Dose	Dose administered in mg at each dosing date collected on the CRF.
Cumulative Dose	Cumulative dose (mg) is sum of the doses (mg) administered to a subject during the treatment period.
Relative dose intensity (%)	Arm1: $\left[\frac{\text{Cumulative dose (mg)}}{(\text{Last dose date} - \text{Start dose date} + 14) \times 240 / 14} \right] \times 100$

Table 7.4.1-2: Administration of Study Therapy: Definition of Parameters

Nivolumab	
	Arm2: $[\text{Cumulative dose (mg)} / ((\text{Last dose date} - \text{Start dose date} + 28) \times 480/28)] \times 100$
Duration of treatment	Last dose date - Start dose date +1

7.4.2 Modifications of Study Therapy

7.4.2.1 Dose delays

Treatment may be delayed for up to a maximum of 6 weeks from the previous dose. Dose interruption of nivolumab which results in treatment interruption of >6 weeks will require treatment discontinuation, with the following exceptions: dosing interruptions to allow for prolonged steroid tapers to manage drug-related adverse events; dosing interruptions for non-drug-related reasons if approved by the medical monitor. Prior to re-initiating treatment in a subject with a dosing interruption lasting >6 weeks, the Medical Monitor must be consulted. A dose will be considered as actually delayed if the delay exceeds 2 days (i.e., greater than or equal to 3 days from scheduled dosing date). The length of delay is defined as (duration of previous cycle in days – 14) for Arm 1 and (duration of previous cycle in days – 28) for Arm 2. Dose delays will be divided into following categories: 3 - <8 days, 8 - <15 days, 15 - <28, 28 - <42, >=42 days. Reason for dose delay will be retrieved from the case report form (CRF) dosing pages.

The following parameters will be summarized by treatment arm:

- Number of dose delayed per subject, length of delay and reason for dose delay
- Number of subjects with at least one dose delay along with reason for the dose delay.

